10.3.1 Procedure related adverse events

Study procedures may involve the placement of a catheter, which may lead to allergic reaction, redness, swelling, bruising, pain, bleeding or infection at catheter insertion site. The study procedures may also involve the use of adhesive to secure the placement of medical equipment. The adhesive may cause an allergic reaction, inflammation, redness, swelling, or itching when in contact with the skin.

10.3.2 Risks related to repeated blood draws

Subjects will participate in several blood draws throughout the course of the study, which have the potential to cause a venous line-vasovagal response, bruising, tenderness, and rarely infection.

10.4 Follow-up of AEs and SAEs

All AEs should be followed up and subjects will be rendered appropriate medical care and treatment at the discretion of the Investigator until resolution or until the Investigator and Sponsor concludes that further follow-up is not necessary. If the AE has not resolved by the post-treatment follow-up visit, the stop date will be recorded as “ongoing.”

All SAEs should be followed up until resolution or permanent outcome of the event or until the Investigator and Sponsor judge that further follow-up is not necessary.

If information is not available at the time of the first report and becomes available at a later date, the Investigator should complete a follow-up SAE form at the earliest possible time or provide other written documentation and fax/email it immediately within 24 hours of receipt of information to the Sponsor or designee. Copies of any relevant data from the hospital notes (e.g., ECGs, laboratory tests, discharge summary, postmortem results) should be sent accordingly, if required.

All other non-serious AEs must be followed until the outcome of the event is “recovering” (for chronic conditions), or “recovered”, or until the end of the post-treatment follow-up stated in the protocol, whichever comes first, and until all queries related to these AE’s have been resolved.

10.4.1 Safety Reporting to IRBs or IECs, and Regulatory Authorities

The Sponsor or designated qualified vendor will be responsible for reporting all suspected unexpected serious adverse reactions (SUSARs) and any other applicable SAEs to regulatory

authorities, Investigators and IRBs or IECs, as applicable, in accordance with national regulations in the countries where the study is conducted and per the Safety Management Plan.

11.0 DATA HANDLING AND MANAGEMENT

Clinical Data Management (CDM) is the responsibility of the Sponsor or delegate.

11.1 Data Management

The full details of procedures for data handling will be documented in the Data Management Plan (DMP).

AEs and medical history will be coded using the current version of the Medical Dictionary for Regulatory Activities (MedDRA). Concomitant medications will be coded using the current version of the World Health Organization (WHO) Drug Dictionary. The dictionary versions used will be documented in the DMP and recorded in the Study Master File documentation.

Unique numbers will identify the subject and the biological material obtained from the subject. Appropriate measures such as encryption or deletion will be enforced to protect the identity of human subjects in all presentations and publications as required by local/regional/national requirements.

Data from screening failures will be entered into the database.

Laboratory data will be electronically transferred to the responsible Data Management Unit for database reconciliation purposes. The electronic laboratory data will be considered source data. In cases where sensitive non-PK laboratory data is transferred via non-secure electronic networks, data will be encrypted during transfer.

The laboratory will provide one copy of the laboratory reports to the site staff. The site staff will receive all safety laboratory data electronically or based on fax reports directly from the laboratory. An Investigator must review, evaluate, sign, and date the laboratory print-outs upon receipt. The signed print-out of the laboratory reports are source data.

All other results, including PK data and laboratory tests will be transferred electronically to the responsible Data Management Unit.

11.2 Electronic Case Report Forms

11.2.1 Clinical Data Management Workflow

eCRFs will be developed by the Sponsor or delegate's CDM or an authorized CDM department, in collaboration with the clinical study team and statistician. CDM will document the process workflow in the DMP. After data entry, monitor(s) will source data verify (SDV) the eCRFs against the source documents. Queries may be issued to clarify the data entered. The Principal Investigator will electronically sign the eCRFs after all data have been entered and all queries have been resolved. If corrections and/or resolution of queries are required after Principal Investigator approvals, those eCRFs affected by changes will be re-signed by the Principal Investigator. The database may be locked after the Principal Investigator approvals are completed.

11.2.2 Data Entry of eCRFs

Data required for analyses and subject safety assessments will be entered from source documentation into eCRFs. Instructions for data entry will be provided in the eCRF Completion Guidelines. All site staff involved with entering data into the eCRFs will be trained prior to gaining access to the study database.

11.2.3 Corrections to eCRFs

Queries may be generated by the eCRF system during data entry, and queries may be generated by CDM staff, monitors, Principal Investigators, the Sponsor, and other data reviewers during the course of the study. Only specific site personnel will be authorized to make corrections to the eCRFs; CDM will ensure personnel are trained prior to granting access in the eCRF system. Corrections will be made directly in the eCRF – by modifying existing data, adding new data, or deleting data, as appropriate. All data corrections will be logged in the electronic audit trail.

11.2.4 Principal Investigator Approval of eCRF Data

The Investigator or Investigator's authorized staff must ensure that all information derived from source documentation is consistent with the source information and accurately reflected in the eCRFs. By electronically signing the eCRFs, the Investigator confirms that the information is complete and correct.

11.3 Retention of Documents

At the completion of the study, all records created by and under the supervision of the Investigator should be maintained in accordance with the requirements of the regulatory authority guideline and the GCP Guideline. These will be available for inspection at any time by the Sponsor or the FDA.

Clinical study documents are archived upon completion of the study and maintained for at least 15 years from the study closure or longer in accordance with local regulation and applicable regulatory authority guidelines, and the study Sponsor will be notified prior to destruction of study records.

Current FDA guidelines require records to be retained for a period of 2 years following the date a marketing application is approved for the drug, for the indication for which it is being investigated. If no application is filed or if the application for the investigated indication is not approved, documents will be kept for a minimum of 2 years after the investigation is discontinued and the FDA is notified.

12.0 STATISTICAL METHODS

12.1 Statistical and Analytical Plans

A statistical analysis plan (SAP), including the statistical analysis and tables/listings/figures will be developed. Subjects who are randomized into the test (LC350189 50 mg, LC350189 100 mg, or LC350189 200 mg) or placebo groups before the Protocol version 5.0 will be combined and analyzed with subjects who will be enrolled after the implementation of the Protocol version 5.0. For subjects randomized into the active control group before the implementation of the Protocol version 5.0, the active control group will be listed and can be summarized for exploratory purpose and further details will be described in a SAP.

12.2 Study Endpoints

The study endpoints are measured or derived parameters used to assess whether the study objectives have been met. The endpoints for this study are shown in [Table 12-1](#). Additional endpoints may be added to the SAP as needed to address the needs of the study.

Table 12-1 Study Endpoints

Primary Objective	Endpoint
To assess the efficacy of LC350189 in terms of sUA level <5 mg/dL at Week 12 (Day 84) to find therapeutic dose of LC350189.	
Proportion of subjects who achieve sUA level <5.0 mg/dL at Day 84 (Visit 8).
Secondary objectives	Endpoints
To assess the efficacy of LC350189 in terms of sUA levels	
Proportion of subjects with sUA <6.0 mg/dL at Day 84 (Visit 8).Proportion of subjects who achieve sUA <5.0 mg/dL at each visit.Proportion of subjects with baseline (Visit 4) sUA >10 mg/dL who achieve <5.0 mg/dL at Day 84 (Visit 8).Proportion of subjects with baseline (Visit 4) sUA >10 mg/dL who achieve <6.0 mg/dL at Day 84 (Visit 8).Proportion of subjects per renal function at baseline (Visit 3) who achieve sUA <5.0 mg/dL at Day 84 (Visit 8).Proportion of subjects per renal function at baseline (Visit 3) who achieve sUA <6.0 mg/dL at Day 84 (Visit 8).
To investigate the PK and PD characteristics of LC350189 in subjects with hyperuricemia and a diagnosis of gout.	
$C_{trough,ss}$ at baseline (Visit 4), Day 14 (Visit 5), Day 28 (Visit 6), Day 56 (Visit 7) and Day 84 (Day 8).Change and percent change in sUA levels from baseline (Visit 4) at each visit.Maximum percent reduction in sUA level during treatment.
To assess antiflare activity in subjects in subjects with hyperuricemia and a diagnosis of gout.	
Gout flare rate in subjects.Gout flare rate in subjects with sUA <6.0 mg/dL at Day 84 (Visit 8).Proportion of subjects receiving gout flare rescue treatment.

Exploratory objectives	Endpoints
To explore the metabolic and anti-inflammatory effects of LC350189.	
Change in HbA1c from baseline (Visit 4) to Day 84 (Visit 8).Proportion of subjects with HbA1c <7% at Day 84 (Visit 8).Proportion of subjects with HbA1c ≤6.5% at Day 84 (Visit 8).Change in FPG from baseline (Visit 4) at Day 84 (Visit 8).Change in hs-CRP from baseline (Visit 4) at Day 84 (Visit 8).Serum concentrations of hypoxanthine and xanthine at baseline (Visit 4) and Day 84 (Visit 8).
Safety Objectives	Endpoints
To assess the safety and tolerability of LC350189	
Adverse eventsLaboratory valuesVital signsECG

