--	--

Table 2-1 Schedule of Assessments

Study Period ¹	SCREENING & WASH-OUT/PROPHYLAXIS ²			TREATMENT PERIOD ³				End of treatment/ early termination	FOLLOW-UP
				—					
Visit number	1	2	3	4	5	6	7	8	9
Time point (Weeks)	-5 to -3 ⁴	-5 to -3 ⁴	-2 to -1	1	2	4	8	12	14
Time point (Days)	-33 to -26	-30 to -23	-9 to -4	1	14 (±2D)	28 (±2D)	56 (±2D)	84 (±2 D)	98 (±2 D)
Informed consent	X								
Assess eligibility criteria	X ⁵	X		X ⁶					
Demographics	X								
Medical history	X								
Physical examination	X								
Height	X								
Weight, BMI	X			X	X	X	X	X	X
Tophi assessment	X								X
Pregnancy test ⁷	X ⁸			X	X	X	X	X	
Hep B, Hep C, HIV test	X								
Record prior ⁹ /concomitant medications	X		X	X	X	X	X	X	X
12-lead ECG	X			X					X
Vital signs	X ¹⁰		X	X ¹¹	X	X	X	X	X
Blood sampling for endpoints and laboratory tests	X ⁴		X ⁵	X ¹²	X	X	X	X	
Blood sampling for PK/PD ¹³				X	X	X	X	X	
Urine sampling - urinalysis	X		X	X	X	X	X	X	
sUA blood sampling for randomization			X ⁵						
Randomization				X ^{14,15}					
Dispense prophylaxis ¹⁶		X		X		X	X		
Dispense study drug				X		X	X		
Collect unused prophylaxis				X		X	X	X	
Collect unused study drug						X	X	X	
Drug accountability/compliance				X ¹⁷		X	X	X	
Assess and record adverse events	X	X	X	X	X	X	X	X	X
Gout Flare eDiary ¹⁸		X ¹⁹	X	X	X	X	X	X	
eDiary device return									X

¹. Subjects will be instructed to attend all Visits following a fast for at least 8 hours except visit at Day 98 (Visit 9).

². All efforts should be made to maintain protocol-defined visit windows, but if an extenuating circumstance arises preventing this, the Sponsor and/or designee should be consulted. If the Sponsor and/or designee determine that the scientific integrity of data and subject safety would not be compromised, an out of window visit may be permitted.

³. Subjects will be instructed to withhold the investigational products on Visit days.

⁴. Screening Visit will be between Day -33 to -26; prophylaxis will start between Day -30 to -23, once a subject is confirmed eligible. Subjects will be instructed to discontinue their current ULT the same day they begin prophylaxis if they are on ULT at screening.

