During the treatment period, subjects will orally self-administer LC350189 or its placebo for 12 weeks starting on Day 1. To maintain consistency, patients will be instructed to take the investigational product at the same time daily, and to withhold the investigational product until after pre-dose laboratory sampling on the days of scheduled visits (Days 14, 28, 56, and 84). At each visit during the treatment period, blood will be sampled for primary, secondary and exploratory endpoint evaluations, and safety assessments will be performed ([Table 12-1](#)). On Day 1 (Visit 4) PK/PD analysis will be conducted pre-dose and 4 hours post-dose for sparse data. For dense data, additional 2, 8 hours and 12 hours post-dose in subjects, who sign written informed consent for dense PK/PD sampling, will be collected on Day 1. On Day 14 and 28 (Visit 5 and 6), PK/PD analysis will be conducted pre-dose for both sparse and dense data. On Days 56 (Visit 7), blood will be sample at pre-dose and 4 hours post-dose for sparse data; and additional 8 hours post-dose for dense data. On Day 84 (Visit 8), pre-dose blood will be sampled at a single time point for PK trough and PD analyses for both sparse and dense data.

Subjects will record the incidence of gout flares using electronic patient diaries (eDiary) from start of prophylaxis (Visit 2) through to end of treatment (Visit 8).

Subjects enrolled to the study before the implementation of the Protocol version 5.0

[figure not shown]
Upon implementation of the Protocol version 5.0, enrollment to the active control group (febuxostat) will be stopped and subjects will be randomized to one of four groups (LC350189 50 mg, LC350189 100 mg, LC350189 200 mg, or placebo).

Subjects who have already randomized to the active control group (febuxostat) on Day 1 (Visit 4) before stopping enrollment of the active control group will stay in the study and continue receiving the treatment regimen (one capsule from each of 2 bottles of LC350189 placebo and 1 bottle of febuxostat 40 mg or 80 mg) that they are initially assigned to. The subjects will receive febuxostat 40 mg on Day 1 (Visit 4) and continue to be on febuxostat 40 mg for the rest of the treatment period if their sUA is < 6.0 mg/dL on Day 14 (Visit 5). If their sUA is \geq 6.0 mg/dL on Day 14 (Visit 5), they will receive febuxostat 80 mg QD on Day 28 (Visit 6) and will continue to be on this dose for the rest of the treatment period.

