#### **8.1.3. Other Efficacy Endpoints**

Change from baseline to Day 84 (Visit 8) in HbA1c, in fasting plasma glucose (FPG), and in high-sensitivity C-reactive protein (hs-CRP) will be summarized. Missing values will be imputed with Last Observation Carried Forward (LOCF) method.

Proportions of subjects with HbA1c < 7% at Day 84 (Visit 8) and proportions of subjects with HbA1c <= 6.5% at Day 84 (Visit 8) will be summarized, where dropout subjects will be considered as not meeting the criteria.

Serum concentrations of hypoxanthine and xanthine will be summarized by visit.

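### LOCF in SAP 8.1.3 lets an earlier value stand as the 12-week HbA1c, FPG or hs-CRP result, which biases the estimated change and makes its interval too narrow

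*Protocol*

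**What the plan says.** Protocol 12.2 (Table 12-1) lists "Change in HbA1c from baseline (Visit 4) to Day 84 (Visit 8", "Change in FPG from baseline (Visit 4) at Day 84 (Visit 8" and "Change in hs-CRP from baseline (Visit 4) at Day 84 (Visit 8". SAP 3.2.4 repeats them. Each names two time points, whereas change in sUA is defined at every visit.

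For missing data on these three changes, SAP 8.1.3 says "Missing values will be imputed with Last Observation Carried Forward (LOCF) method". It does not say whether baseline counts as an observation that may be carried. The Full Analysis Set (SAP 4.4.3) requires one dose and no post-baseline value.

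On sampling, Protocol 6.1 says "At each visit during the treatment period, blood will be sampled for primary, secondary and exploratory endpoint evaluations", and the row "Blood sampling for endpoints and laboratory tests" in Table 2-1 is marked at Visits 4 to 8. A footnote adds "Subjects will be instructed to attend all Visits following a fast for at least 8 hours except visit at Day 98 (Visit 9". Glucose is in the chemistry panel (Protocol Table 9-1), and SAP 9.2 grades it as a fasting analyte. HbA1c and hs-CRP are not in Table 9-1, and neither document lists their assay visits. Table 2-1 also carries the heading "End of treatment/ early termination", apparently over Visit 8.

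SAP 8.1 plans ANCOVA for change from baseline and includes Section 3.2.4 in its scope. SAP 8.1.3 says only that these changes are summarized. The sensitivity analysis in SAP 8.2 covers the primary endpoint alone and itself uses LOCF.

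**The concern.** The endpoint is a 12-week change. LOCF puts in its place a value that is not from week 12, and the analysis then treats that value as measured.

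Which value is carried depends on facts that the documents leave open:

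- If HbA1c and hs-CRP are assayed only at Visits 4 and 8, and baseline may be carried, a subject without a Visit 8 value is scored as zero change.
- If they are assayed at each visit, a Day 14, 28 or 56 value becomes the Day 84 result. The same holds for FPG, where interim fasting glucose is collected.

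The rule does not touch dropouts alone. Protocol 9.1.20 allows missed visits during the pandemic and limits local laboratories to safety assessment, so a subject still on treatment can also lack a Day 84 value.

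At stake are the size of the estimated effect on these markers and the precision claimed for it. The protocol includes them to inform later studies (Protocol 6.3).

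**Working it through.** **Inputs from the plan.** Protocol 12.4 gives 38 subjects per arm and 20% dropout. Its calculation reproduces: (1.96 + 0.84)² × (0.80×0.20 + 0.47×0.53) / 0.33² = 29.45, rounded up to 30; 30/0.80 = 37.5, rounded up to 38. The plan gives no SD or effect size for the three markers.

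**Assumptions.** Results are in units of the SD of change (SD = 1). True difference μ is 0 to 0.8, placebo mean change is 0, and dropout share d is equal in the arms and unrelated to outcome.

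**Case A: every dropout scored zero.**

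- Expected difference = (1 − d)μ, that is 0.95, 0.90, 0.80 and 0.70 of the true value at d = 5, 10, 20 and 30%.
- Active-arm variance = (1 − d) + d(1 − d)μ²; placebo variance = 1 − d.
- At d = 0.20, μ = 0.5: SE = √[(0.84 + 0.80)/38] = 0.208. For completers, SE = √[2/(38×0.8)] = 0.256. The ratio is 0.81. Over μ = 0 to 0.8 it runs from 0.80 to 0.83.
- Against complete data on all 38 per arm, the ratio is 0.89 to 0.92. The interval is thus narrower than it would be with no dropout at all.
- z: 0.5/0.256 = 1.95 for completers and 0.4/0.208 = 1.93 with zeros.
- Coverage of the true 12-week difference: the bias is dμ = 0.10, or 0.10/0.208 = 0.48 SE, so coverage is Φ(1.48) − Φ(−2.44) ≈ 92%. The same steps give about 94% at μ = 0.3 and 88% at μ = 0.8. Simulation agrees. Intervals from observed values cover about 95%.

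**Case B: interim values carried.** Assume that 30, 50 and 85% of the full effect is present at Visits 5, 6 and 7. Assume also that dropouts are spread evenly over no post-baseline value (baseline carried) and last value at Visit 5, 6 or 7. The mean fraction carried is (0 + 0.30 + 0.50 + 0.85)/4 = 0.41, so the expected difference is 0.80 + 0.20×0.41 = 0.88 of the true one.

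A simulated ANCOVA (38 per arm, 20% dropout, true difference 0.5, correlation between visits 0.7, 4,000 runs) gave:

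| Data used | Estimate | SE |
|---|---|---|
| All 38 per arm observed | 0.50 | 0.212 |
| Completers | 0.50 | 0.238 |
| All dropouts zero | 0.40 | 0.195 |
| Interim carry-forward | 0.44 | 0.209 |

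In the last row effect and SE are both about 0.88 of the completer figures. The SE is 0.99 of the full-data SE, as though almost nobody had dropped out.

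**Case C: unequal dropout, with a change c common to both arms.** Scoring dropouts zero gives (1 − d_T)(c + μ) − (1 − d_P)c. With c = 0.5:

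- μ = 0.5, dropout 10% active and 30% placebo: 0.9×1.0 − 0.7×0.5 = 0.55, an inflation.
- μ = 0.5, dropout 30% and 10%: 0.7×1.0 − 0.9×0.5 = 0.25.
- μ = 0, same two patterns: +0.10 and −0.10.

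**The case against.** A reader might infer that every dropout is scored as exactly zero on all three markers. The documents do not support that. Protocol 6.1 and the endpoint-blood row point to sampling at Visits 4 to 8. For FPG, interim fasting glucose is plainly available. Endpoint wording does not fix sampling times: the primary endpoint is also defined only at Day 84, yet sUA is drawn at each visit. Exact zero further requires that baseline may be carried, which the SAP does not say. This part of the objection stands. For HbA1c and hs-CRP the question stays open, because the Protocol 6.1 sentence cannot hold for every exploratory assay: SAP 10.3.1 has hypoxanthine and xanthine analysed at Visits 4 and 8 only.

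A reader might also infer that LOCF always pulls the result towards no effect. Case C shows that it need not.

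A third tempting reading is that an early-termination sample will be analysed as Day 84. This rests on a column heading that the SAP's copy of the schedule lacks. Protocol 6.4.3 asks discontinuing subjects for the Visit 9 tests among others, and no endpoint blood is marked at Visit 9. The mapping is unstated, not established.

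The plan already offers partial protection: efficacy is also analysed on the Per-Protocol Set, from which early withdrawals without Week 12 data may be excluded (SAP 4.4.4). An observed-value analysis also has a weakness of its own, since it conditions on having a Day 84 value. Neither point justifies treating a carried value as observed in the main analysis.

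**Conclusion.** The concern holds in a limited form. SAP 8.1.3 sets LOCF for endpoints defined as 12-week change. On either reading of the sampling schedule, where a value is carried it is treated as a Day 84 measurement. The estimate is then biased, and the interval is narrower than the observed values support.

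With equal 20% dropout and no placebo change, effect and SE are both about 0.80 of the completer figures in the all-zero case. They are about 0.88 with interim carry-forward, which depends on the assumed onset profile. The 0.80 figure is a worst case, not a forecast. Direction is not fixed once dropout differs between arms and both arms share a change. Because effect and SE shrink together when dropout is equal, z hardly moves; in that setting the damage is to the size and stated precision of the effect rather than to significance.

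Severity is low. The endpoints are exploratory, SAP 2.3 allows them to be left out of the study report, and SAP 8.1 describes the trial as not rigorously confirmatory.

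**What to change.** Rewrite the missing-data paragraph of SAP 8.1.3 for HbA1c, FPG and hs-CRP:

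- State at which visits each marker is assayed.
- Replace LOCF with the ANCOVA of SAP 8.1 (treatment, strata, baseline) on observed on-treatment Day 84 values, and say that it applies to these endpoints.
- Give an analysis window for Day 84 that keeps the out-of-window visits allowed by Protocol 9.1.20 while treatment continues. The ±5 days in SAP 4.4.4 is an inclusion rule for the Per-Protocol Set, not a visit window.
- State that an earlier early-termination sample is not mapped to Day 84.
- As sensitivity analysis, add multiple imputation that uses any interim values, or a repeated-measures model if interim values exist.

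The cost is one SAP paragraph, fewer subjects in the Day 84 tables, slightly wider intervals, and reliance on a missing-at-random assumption, which should be stated.
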